#### 7.1.5 Conventions for Missing Concomitant Medication Dates

If start date and stop date are missing, medication will be assumed to occur both prior and concomitantly. Also see Section 7.6.

# 7.2 Analysis Sets

# 7.2.1.1 *Safety Set*

The Safety Set will include all randomized subjects who receive at least 1 dose of double-blind study medication. Subjects in this analysis set will be used for demographic, baseline characteristics, and safety summaries. Subjects will be analyzed according to the actual treatment received.

#### 7.2.1.2 PK Set

The PK Set will include all randomized subjects who receive at least one dose of double-blind study medication and who have any available plasma concentration data. Subjects will be analyzed according to the actual treatment received.

#### 7.2.1.3 PD Set

The PD set will consist of all subjects who receive at least 1 dose of study drug and have at least 1 postdose PD result. Subjects will be analyzed according to the randomized treatment.

## 7.3 Disposition of Subjects

Study Information, including date first subject signed ICF, date of last subject's last visit/contact, date of last subject's last procedure for collection of data for primary endpoint, MedDRA Version, WHODrug Version, SAS Version, will be listed.

Disposition of all screened subjects (denominator) will be tabulated (count and percent); there will be no inferential analysis of subject disposition data.

Disposition of all randomized subjects will be tabulated:

• All subjects received at least one dose of study drug (denominator).

- Subjects who completed the study.
- Subjects who prematurely discontinued study.

Primary reasons for discontinuation of study as entered on the electronic case report form (eCRF), will be tabulated. Reasons for discontinuation include adverse event, liver function test, significant protocol deviation, lost to follow-up, voluntary withdrawal, study termination, and other. The date of first dose, date of last dose, duration of treatment and the reason for premature discontinuation of study drug/study visit will be presented for each subject in listings.

Disposition of screen failure subjects will be summarized descriptively. Primary reasons for failure will be summarized and will be presented in a data listing.

Significant protocol deviations will be summarized and listed.

All summaries will be presented by treatment sequence and overall.

# 7.4 Demographic and Other Baseline Characteristics

Demographics and baseline characteristics including age, gender, race, and body mass index will be listed and summarized by randomized treatment sequence and overall based on the Safety Set.

Baseline values for primary and secondary PD assessments (including average % of conditioned responses during the EBC test at Day 8, MMN amplitude at Fz at Day 8, P300 amplitude at Pz at Day 8, ASSR at Cz at Day 8, BACS cognitive battery composite score at Day 7, plasma D-serine, L-serine levels and the ratio of the two at Day 8) will also be summarized by treatment sequence and overall based on the Safety Set.

#### 7.5 Medical History and Concurrent Medical Conditions

Medical history and concurrent medical conditions will be coded using the Medical Dictionary for Drug Regulatory Activities (MedDRA, version 18 or higher) coding system. Ongoing conditions are considered concurrent medical conditions.

All medical history and concurrent medical condition data will be listed by site (study center) and subject number. The listing will contain subject identifier, treatment sequence, system organ class (SOC), preferred term (PT), whether there was any medical history or concurrent condition, and, if yes, a detail of the medical history or concurrent condition.

Medical history and concurrent medical conditions will be listed and summarized by each treatment sequence and overall based on the Safety Set.

# 7.6 Medication History and Concomitant Medications

All medication history and concomitant medications will be listed by site (study center) and subject number. The listings will contain subject identifier, treatment, World Health Organization Drug Dictionary (WHODrug) preferred medication name, dose, unit, frequency, route, start date, stop date, whether the medication was ongoing, and reason for use. No inferential statistics will be presented.

Medication history and concomitant medications will be coded using the WHODrug Version 01March 2017 or higher.

# 7.7 Study Drug Exposure and Compliance

The duration of exposure will be summarized as a continuous variable.

The percentage of study drug compliance will be defined as {(number of tablets dispensed – number of tablets returned) / [5\*(date of last dose – date of first dose +1)]} x 100%. For each treatment group, study medication compliance will be summarized by compliance category (<80%, 80 to 120%, and >120%) and the number of subjects in each compliance category. Study medication compliance will also be summarized as a continuous variable using descriptive statistics (n, mean, SD, median, minimum, and maximum) for each treatment group.

All study drug administration and compliance data will also be summarized in a listing(s).

# 7.8 PD Analysis

# 7.8.1 Primary PD Endpoint

The primary endpoint is the average % of conditioned responses in the EBC task at Day 8.

The primary endpoint will be summarized for baseline, post-dose, and change from baseline by treatment.

Pairwise comparisons between active treatments and placebo will be generated within the framework of analysis of variance (ANOVA), with treatment sequence, period, and treatment as fixed effects. Subject nested within sequence is included as a random effect. The dependent variable is the change in response from the period baseline assessment to the final treatment day for each period, and the response data will be logit transformed before the change is calculated. The analysis will be performed using observed data. Potential carryover effects will be investigated. P-values and confidence intervals will be reported. The following SAS code may be used:

```
proc mixed data=XXXX;
class sequence treatment period subject;
model response = sequence treatment period / ddfm=kr;
random subject (sequence);
estimate 'Treatment Difference' treatment -1 1 / al alpha = 0.10 E;
lsmeans treatment;
run;
```

The primary endpoint will be tested individually for each of the two doses against 5% (one-sided) level of significance.

As a supplementary analysis, an ANCOVA (analysis of covariance) model will be applied to the primary endpoint with (period) baseline as a covariate, treatment sequence, period, treatment effect, baseline-by-treatment as fixed effects, and subject as a random effect. The dependent variable is the change in response from the period baseline assessment to the final treatment day for each period, and the response data will be logit transformed before the change is calculated. Based on a missing at random assumption, this analysis will be performed using observed data only. P-values and confidence intervals for this model will be provided.

In addition, as a supporting analysis and in the interim analysis (see Section 7.12), the primary endpoint will be analyzed using a Bayesian normal linear model with treatment sequence, period, and treatment as fixed effects, subject within sequence as a repeated factor, and (period) baseline as a covariate. The dependent variable is the change in response from the period baseline assessment to the final treatment day for each period. The response data will be logit transformed before the change is calculated. A diffuse normal distribution will be used as a prior for the regression coefficients and a diffuse inverse gamma for the residual variance. The Bayesian model will be used to estimate the posterior distribution of the treatment effect from each dose (as applicable). The posterior mean, standard deviation and the 90% credible interval (highest posterior density interval) for each treatment, along with the posterior mean treatment difference, corresponding standard deviation and 90% credible interval (highest posterior density interval) will be reported. The following SAS code may be used for the analysis:

proc genmod data = XXXX;

class Sequence Period Treatment Subject;

model Response = Sequence Period Treatment Subject Baseline / dist = Normal link=identity alpha=0.1;

bayes seed = 666 coeffprior=normal dispersionprior = igamma(shape=0.001, scale=0.001) nbi=2000 nmc=10000 maxit=2000 outpost=post diagnostics=all stats=all;

lsmeans Treatment / pdiff alpha = 0.1;

run;

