11.1.4 PD Analysis

11.1.4.1 Analysis of Primary PD Endpoint

Pairwise comparisons between active treatments and placebo will be generated within the framework of analysis of variance (ANOVA), with treatment sequence, period, and treatment as fixed effects. Subject nested within sequence is included as a random effect. The dependent variable is the change in response from the period baseline assessment to the final treatment day for each period. The analysis will be performed using observed data. Potential carryover effects will be investigated. P-values and confidence intervals will be reported.

A frequentist analysis will be done for the full data set, using simulations to adjust for the effect of the interim analysis on the type I error rates. The results of the primary endpoint will be considered statistically significant at either of the 2 doses (as applicable) if the one-sided p<0.05, without adjustment for multiplicity (ie, the type I error rate will be separately controlled for each dose).

In addition, the primary endpoint will be analyzed using a Bayesian normal linear model with treatment sequence, period, and treatment as fixed effects and subject within sequence as a repeated factor. The dependent variable is the change in response from the period baseline assessment to the final treatment day for each period. The response data will be logit transformed before the change is calculated. A diffuse normal distribution will be used as a prior for the regression coefficients and a diffuse inverse gamma for the residual variance. The Bayesian model will be used to estimate the posterior distribution of the treatment effect from each dose (as applicable).

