#### 7.12 Interim Analysis

A planned unblinded interim analysis of the primary PD endpoints will be conducted when approximately 14 patients have been completed the primary endpoint. The site will be allowed to continue enrollment to the high/placebo comparison, with the goal that approximately 16 patients will be randomized by the time the interim analysis is complete. (The additional approximately 2 subjects will be included in the final analysis but not the interim analysis.) The interim PD analysis will be to determine whether to continue enrolling subjects to the high-dose/placebo comparison or switch enrollment to the low-dose/placebo comparison.

The Bayesian normal linear model described in Section 7.8.1 will be performed for the primary endpoint. "Success Stop criteria" at interim analysis is 70% posterior probability (or greater) of a difference between 500 mg TAK-831 and placebo >0.6 (on logit scale), and a decision of switching to the low dose will be made when "Success Stop criteria" are met. "Futility Stop criteria" will be met if the posterior probability of a difference between 500 mg TAK-831 and placebo >0.1 (on logit scale) is less than 30%, and a decision of switching to the low dose will be made. If none of the aforementioned criteria are met, a decision of continuing enrolling high-dose/placebo subjects ("Continue" decision) will be made.

In addition, a decision to switch to the low dose may be made based on the safety or tolerability of the high dose.

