# 7.13 Changes in the Statistical Analysis Plan

The primary endpoint will be tested individually for each of the two doses against 5% (one-sided) level of significance.

The summaries of safety parameters will be presented by placebo, each TAK-831 dose level, and TAK-831 overall (as appropriate), rather than by cohort as stated in the protocol.

To increase statistical efficiency, baseline will be used as a covariate in the Bayesian normal linear model described in Section 7.8.1.

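### The decisive primary test leaves out period baseline as a covariate; adding it, split into between- and within-subject parts, is a low-cost change that could sharpen a comparison of about 16 subjects

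*SAP*

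**What the plan says.** SAP 7.8.1 defines the outcome of the decisive test: "The dependent variable is the change in response from the period baseline assessment to the final treatment day for each period", with the response logit transformed first. Sequence, period and treatment are fixed effects and subject within sequence is random. The code has no baseline term: "model response = sequence treatment period / ddfm=kr". Each dose is tested separately at one-sided 5%. The section adds: "Potential carryover effects will be investigated".

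Period baseline enters two other analyses.

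- The supplementary ANCOVA ("As a supplementary analysis, an ANCOVA (analysis of covariance) model will be applied to the primary endpoint with (period) baseline as a covariate") also carries a baseline-by-treatment term. No code, centring or contrast is given.
- The Bayesian model is used at the interim (SAP 7.12) and as a supporting final analysis. It is coded as "model Response = Sequence Period Treatment Subject Baseline / dist = Normal link=identity". Because subject is a fixed class effect there, its baseline slope is already a within-subject slope. SAP 7.13 explains the covariate: "To increase statistical efficiency, baseline will be used as a covariate in the Bayesian normal linear model".

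Protocol 11.1.4.1 plans a frequentist analysis of the full data "using simulations to adjust for the effect of the interim analysis on the type I error rates". SAP 6.0 plans 16 subjects on the high dose against placebo, then possibly 16 more on either the high or the low dose.

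**The concern.** Analysing change with no baseline covariate fixes the coefficient of baseline at 1. If the true within-subject slope is lower, the change score carries baseline noise that a fitted slope would remove. The SAP accepts this argument for its Bayesian model but gives no reason for leaving the decisive test unadjusted, so the interim decision and the final test rest on different estimators.

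The supplementary ANCOVA does not fill the gap. With a baseline-by-treatment term, the treatment coefficient depends on the baseline value at which it is evaluated, and none is stated.

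The low dose would have at most 16 subjects, and the high dose about 16 if enrolment switches. At that size a variance cut of 10% to 40% matters, and the data needed are already collected.

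**Working it through.** **Inputs from the documents.** n = 16 per dose comparison, or 32 if the high dose continues; one-sided 5%; effect size 0.6, defined as mean difference over the SD of that difference (SAP 6.0).

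**Assumed, because the documents do not give them.** Two balanced sequences, complete pairs, normal data. r is the correlation between the between-period difference in baseline and the between-period difference in Day 8 response. k is the ratio of their SDs, Day 8 over baseline.

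r is not test-retest reliability. If all four measurements share one common correlation, r is 0 however large that correlation is.

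**Reference power.** The plan states no power. A t test on within-subject differences has noncentrality 0.6 × √16 = 2.4 on 14 df, giving power 0.738; at n = 32 it is 0.953.

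**Variance of the adjusted effect relative to the change-score effect**

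k²(1 − r²) / (k² + 1 − 2rk) × [1 + 1/(n − 4)]

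The bracket is the expected cost of estimating one slope; at n = 16 it is 13/12. At k = 1 the ratio is (1 + r)/2 × 13/12. At r = 0.4, for example, 0.7 × 13/12 = 0.758, a reduction of 24.2%. Percentage reduction at n = 16 (negative means a loss):

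| k | r = 0 | 0.4 | 0.6 | 0.8 | 0.9 |
|---|---|---|---|---|---|
| 0.8 | 58 | 42 | 35 | 31 | 34 |
| 1 | 46 | 24 | 13 | 2.5 | −3 |
| 1.2 | 36 | 11.5 | 0 | −8 | −6 |
| 1.5 | 25 | 0 | −8 | −3 | 16 |

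Simulation reproduced the k = 1 row.

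**Shape and floor.** The gain is larger when Day 8 is less variable than baseline. As k rises above 1 the gain falls to its worst at k = 1/r (true slope rk = 1) and then rises again, as the r = 0.9 column shows. The largest expected loss is 1/(n − 4): 10% at n = 14, 8.3% at n = 16, 3.6% at n = 32. Counting the lost degree of freedom, squared interval width at n = 16 loses at most about 9.5%.

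**The split matters.** The table applies to a within-subject slope. A single unsplit baseline in a random-subject model mixes within- and between-subject slopes. In a rough REML check (1,000 runs per cell, 75% of variance between subjects), the unsplit covariate gained 22, 14 and 8% at r = 0, 0.4 and 0.6, against 42, 24 and 14% when split.

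**Which r is plausible.** Day −1 to Day 8 is 8 days, since there is no Day 0. The Period 2 baseline falls 13 to 20 days after Period 1 Day 8. If serial correlation decays exponentially around a stable subject level (an assumption), r is at most 13/21 = 0.62 or 20/28 = 0.71, a gain of at least 12% or 7% at k = 1. A Period 2 shift that varies between subjects, such as retained conditioning, raises r.

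**Power, as t tests on within-subject differences.** At n = 16 and k = 1 the adjusted test has 0.925, 0.84, 0.79, 0.745 and 0.73 at r = 0, 0.4, 0.6, 0.8 and 0.9, against 0.74 unadjusted. At rk = 1 it is about 0.71.

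**The coded model is not that t test.** If the mixed-model software bounds the subject variance at zero (assumed default; the code does not override it), the fit sometimes pools the two error strata and uses 28 residual df. For the planned ANOVA at n = 16 this gives power of about 0.78 and type I error of about 0.06 when change scores are uncorrelated between periods, and about 0.79 and 0.06 at correlation −0.1. The variance ratios are unaffected, but the power differences need re-simulation with the actual models.

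**Carryover.** Suppose a constant carryover, a fraction c of the effect, shifts both Period 2 measurements after active drug. The change score cancels it. The adjusted estimate has expectation 1 − c(1 − rk)/2 of the truth. At c = 0.5 and k = 1 that is 75, 85, 90 and 95% at r = 0, 0.4, 0.6 and 0.8, with power of about 0.70 to 0.73.

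**Interim rule.** With the SAP 7.12 thresholds, 14 subjects at interim and the change-contrast SD assumed between 0.7 and 1.68 logits, high-dose type I error at nominal 5% was 4.3–5.9% for the change-score test and 4.6–6.1% for the adjusted one. The adjusted test was higher in every cell, by 0.03 to 0.5 points.

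**The case against.** The strongest defence is that the planned choice suits the endpoint. Protocol 9.2.13 describes eyeblink conditioning as a learning measure, and subjects take it four times. Conditioning retained from Period 1 could shift the Period 2 baseline even after the drug has washed out, and only the change score cancels a constant shift of that kind. This stands: it is why the change-score ANOVA should stay in the plan, and with material carryover there is no power gain.

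Second, the Bayesian model already comes close to the proposed analysis, and SAP 6.0 ties the sample size to Bayesian analyses. That narrows the point to which analysis is decisive, but it also shows that the SAP's own efficiency argument applies to the primary test.

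Third, the benefit cannot be fixed from the documents: the grid runs from +58% to −8%. That stands too.

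A reader might go further and infer that the planned test is biased or invalid because it omits baseline. The documents do not support this: the change-score contrast is unbiased, and at fixed n both difference-based tests hold 5% (simulated 0.048 to 0.052). The type I error of about 0.06 for the coded model comes from an assumed variance bound, not from the missing covariate. Nor do the documents support a promised gain of 46%, or of 5 to 19 power points; those need particular values of r and k, the split baseline, no carryover and a difference-based test.

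**Conclusion.** The point holds as a low-cost improvement, mainly in precision. With 16 complete pairs and k = 1, the expected variance of the treatment effect falls by about 46, 24, 13 and 2.5% at r = 0, 0.4, 0.6 and 0.8, and rises by 3% at r = 0.9. Apart from carryover, the downside is limited to an expected 8.3% at n = 16. These figures rest on assumed r and k and on splitting the baseline. Confidence is medium, because the true slope and the size of any carryover are unknown. If rk is near 1 or carryover is material, the change-score ANOVA is as good or better, so it remains a defensible choice if the sponsor states that reason.

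**What to change.** - Make the primary model treatment, period, sequence and period baseline, with baseline split into subject mean and within-subject deviation, random subject within sequence, and no baseline-by-treatment term. For complete pairs an ANCOVA on within-subject period differences gives the same adjustment and avoids the zero bound on the subject variance.
- Keep the change-score ANOVA as a prespecified sensitivity analysis, read together with the planned carryover investigation.
- In the supplementary ANCOVA, drop the interaction or state the baseline value at which treatment is tested.
- Have the model fixed by staff blind to the interim data, since Protocol 1.0 leaves a sponsor group unblinded during the study.
- Run the Protocol 11.1.4.1 simulations with the final coded model, including its variance bound and degrees-of-freedom method, and set the final threshold from them.

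The cost is SAP wording and a simulation run, with no new data or visits. The SAP should state the downsides: one degree of freedom, no gain or a small loss when rk is near 1, slightly higher type I error after the interim rule, and loss of the protection against constant carryover.

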## 7.8.2 Secondary PD Endpoint(s)

The secondary EEG endpoints will be analyzed using an ANOVA model similar to that used for the primary endpoint, as described in Section 7.8.1.

The cognitive battery composite score, the BACS, will be analyzed as follows. The primary measure from each test is standardized by creating z-scores whereby the mean of the test session of a healthy participant is set to 0 and the standard deviation set to 1 [2]. A composite score will be calculated by averaging the 4 measures from the BACS used in the study, and then calculating a z-score of the composite. The composite z-score indicates how much higher or lower the participant's cognition is compared to a healthy person. An ANOVA will be performed on the change from baseline for the composite BACS score, using a similar model to that used for primary endpoint.

For each regimen, the concentrations of D-serine, L-serine, and the ratio of D-serine to total serine with change and percent change from Baseline will be summarized at each time point of each dose level using descriptive statistics. In addition, a mixed model for repeated measures (MMRM) will be used on the change from baseline in these concentrations, with sequence, period, treatment and visit as fixed effects, and subject nested within sequence as a random effect. Based on a missing at random assumption, this analysis will be performed using observed case data only. The effect at each time point for each subject is allowed to vary freely and an unstructured covariance matrix is assumed. If the model does not converge, other covariance structures will be considered. Pairwise comparisons between the test regimens (high dose, low dose and placebo) will be made and the CIs for the difference in the LS means will be constructed for Day 8 assessments.

There will be no adjustment for the multiplicity of secondary endpoints.

All secondary PD endpoints will be summarized for baseline, post-dose, and change from baseline by treatment.

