- (c) Assessments on Days 7 and 8 may be performed 1 day before or after (ie, Day 6 or 8 for Day 7 and Day 7 or 9 for Day 8). If the Day 8 assessments are conducted on Day 9, study drug dosing duration will be extended for 1 additional day as well.
- (d) Inclusion/exclusion criteria will be assessed only in Period 1.
- (e) Vital signs, concomitant medications and AE assessment on Days 2 to 6 to be performed only on subjects who attend the clinic site for any reason. Vital signs will be conducted for safety only and will not be entered into the database for these visits.
- (f) Day 8 EBC, ERP, and EEG assessments are to be performed at approximately (\pm 1 hour) the same time as on Day -1, and the Day 7 BACS cognitive battery assessments are to be performed at approximately (\pm 1 hour) the same time of day as on Day -2.
- (g) Procedures to be conducted only in subjects who receive at least 1 dose of study medication and are assessed within 36 hours of the last dose.
- (h) Study drug intake on Days 2 to 6 may be supervised by a caregiver or family member, conducted at the investigator site or supervised by a qualified designee.
- (i) These tests can be repeated at any time at investigator discretion.
- (j) Serum Beta hCG at Screening and at the Final Visit, at other visits urine Beta hCG determination on women of childbearing potential only.

(m) Blood samples (approximately 4 mL) will be collected from each subject for the determination of plasma concentrations of TAK-831 at the following time points: Day 1 (predose and at 0.25 to 2 hours and 3 to 6 hours postdose), Day 7 (predose and at 0.25 to 2 hours and 3 to 6 hours postdose), and Day 8 (predose). One additional blood sample will be collected for subjects at the Early Termination Visit, if applicable. The sampling schedule may change based on emerging data but will not exceed the number of planned samples.

(n) Blood sample (6 mL) will be collected for analysis of plasma concentrations of D- and L-serine immediately following PK blood collections on Day 1 (predose and 3 to 6 hours postdose), Day 7 (predose and 3 to 6 hours postdose), and Day 8 (predose). Time of sample collection, time since last dose administered and time of last meal should be recorded for each sample collection. Samples may be analyzed for other amino acids, but total blood volume collected will not change.

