TAK-831-1004 was a phase 1, randomized, open-label, single-dose, 2-period crossover study designed to characterize the PK of a single dose of 400 mg of TAK-831 and assess the effect of food on the bioavailability of TAK-831 400 mg when administered as four 100 mg oral tablets of the T2 formulation in 15 healthy adult subjects. In the TAK-831-1004 study, there was only a single AE of mild upper respiratory tract infection, judged to be unrelated to study treatment. One subject met criteria for orthostatic hypotension at a single time point without an accompanying report of a dizziness AE. There were no concerning trends in laboratory, ECG, or vital sign data. Treatment with a single oral dose of 400 mg of TAK-831 T2 formulation temporally increased plasma concentration of D-serine, similar to the results obtained in the Study TAK-831-1001. The magnitude and kinetics of the change in plasma D-serine were similar when the drug was administered in either water or nutritional drink. TAK-831 given as a T2 tablet coadministered with the nutritional drink increased mean C_{max} and AUC_∞ values by 35% and 21%, respectively.

TAK-831-1005 is an ongoing investigator and subject blinded, sponsor unblinded, placebo-controlled clinical study progressively assessing independent cohorts of healthy subjects to continue evaluation of the safety, tolerability, PK, and pharmacodynamics (PD) of escalating multiple doses of TAK-831 at doses higher than those achieved in the TAK-831-1001 study. The following study information is preliminary and is based on blinded adverse event data reported by the investigator and blinded safety endpoint data in study TAK-831-1005. Although not expected, these data are subject to change upon finalization following study monitoring, source data

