## **5.1.2** Secondary Endpoints

- MMN amplitude at Fz (electroencephalogram [EEG]) at Day 8.
- P300 amplitude at midline parietal electrode (Pz) (EEG) at Day 8.
- ASSR at midline central electrode (Cz) (EEG) at Day 8.
- BACS cognitive battery composite score at Day 7.
- Plasma D-serine and L-serine levels, and plasma D-serine:total serine ratio at Day 8.
- TAK-831 plasma concentrations.

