## 7.13 Definition of Study Visit Windows

A windowing convention will be used to determine the analysis value for a given study visit that applies to observed data. For each visit, a window will be defined such that the lower and upper bounds of each window is generally the midpoint between 2 consecutive study visits.

More than 1 result for a parameter may be obtained in a visit window. In such an event, the result with the date closest to the scheduled visit day will be used. In the event of 2 observations equidistant to the scheduled visit day, the later of the observations will be used.

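### The serine MMRM in SAP 7.8.2 has no treatment-by-visit term, so its Day 8 treatment difference is one average shared by all visits

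*SAP*

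**What the plan says.** SAP 5.1.2 defines the endpoint at a single day: "Plasma D-serine and L-serine levels, and plasma D-serine:total serine ratio at Day 8". SAP 7.8.2 gives the inferential analysis, an MMRM on change from baseline "with sequence, period, treatment and visit as fixed effects, and subject nested within sequence as a random effect". The same paragraph adds that "The effect at each time point for each subject is allowed to vary freely and an unstructured covariance matrix is assumed", and ends by saying that "the CIs for the difference in the LS means will be constructed for Day 8 assessments".

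No code is supplied for this model, although 7.8.1 supplies code for the primary ANOVA and for the Bayesian model. The list of effects is therefore the only specification. Protocol 11.1.4.2 names no interaction either and leaves further detail to the SAP, which takes precedence under Protocol 11.1.

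Protocol 3.0, footnote (n), schedules five serine samples per period: Day 1 predose and 3 to 6 hours postdose, Day 7 predose and 3 to 6 hours postdose, and Day 8 predose. The Day 1 predose sample is the period baseline (SAP 7.1), which leaves four post-baseline samples on three days.

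**The concern.** The requested contrast is specific to Day 8, but the listed effects do not let the treatment effect differ between visits. Where the SAP wants an interaction it names one: the supplementary ANCOVA in 7.8.1 has "treatment sequence, period, treatment effect, baseline-by-treatment as fixed effects, and subject as a random effect".

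A constant effect is doubtful because the samples differ in kind. Day 1 follows one dose, while Days 7 and 8 follow repeated dosing. Day 8 is predose, whereas other samples are taken 3 to 6 hours after a dose. Protocol 4.2 reports for plasma that "Treatment with a single oral dose of 400 mg of TAK-831 T2 formulation temporally increased plasma concentration of D-serine". It also reports larger CSF D-serine changes after multiple doses than after one, in healthy subjects.

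At stake are the estimate and interval for the only inferential analysis of a stated secondary objective. They would carry a Day 8 label without being Day 8 quantities.

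**Working it through.** The documents state no figure for this analysis, so there is none to reproduce. The structural result in step 1 needs no numerical assumption. All covariances and effect ratios in steps 2 to 5 are assumptions.

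**1. What the listed model estimates.** The expected change at visit t is μ + sequence + period + visit(t) + τ × [active]. Active minus placebo at visit t is τ for every t, whatever the covariance matrix.

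**2. What τ averages.** Let δ(t) be the true treatment effect at visit t and V the covariance between visits within a period. Generalised least squares for the two-period crossover estimates Σ w(t)δ(t), with w = V⁻¹1 / (1′V⁻¹1). The random subject effect does not alter these weights. For AR(1) with three equally spaced visits, V⁻¹1 is proportional to (1, 1−ρ, 1). So ρ = 0.5 gives (1, 0.5, 1)/2.5 = (0.40, 0.20, 0.40).

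The number of visits depends on how visit is read. The window rule in SAP 7.1 (Definition of Study Visit Windows, printed as 7.13) states: "In the event of 2 observations equidistant to the scheduled visit day, the later of the observations will be used". The two Day 7 samples share a date, so this rule keeps the postdose one and leaves three visits, with Day 8 the only trough. If visit means nominal sampling time, there are four time points, two of them postdose.

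| Assumed within-period covariance | Day 8 weight, 3 visits | Day 8 weight, 4 time points |
|---|---|---|
| Exchangeable | 0.33 | 0.25 |
| AR(1), equal steps, ρ 0.5 to 0.8 | 0.40 to 0.45 | 0.33 to 0.42 |
| Correlation 0.2, Day 8 SD twice the others | 0.05 | 0.02 |
| Correlation 0.2, Day 8 SD half the others | 0.77 | 0.71 |

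AR(1) spaced at Days 1, 7 and 8, with daily ρ of 0.5 to 0.8, gives a three-visit weight of 0.29 to 0.33.

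**3. Effect on the estimate.**

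- *Trough differs from postdose* (three visits, Day 1 and Day 7 postdose effects equal). With f = trough effect / postdose effect, reported/true = (1−w₈)/f + w₈. For f = 0.75: w₈ = 0.05 gives 0.95/0.75 + 0.05 = 1.32, and w₈ = 0.77 gives 0.23/0.75 + 0.77 = 1.08. The same formula gives 1.11 to 1.03 for f = 0.9, 1.00 for f = 1, and 0.81 to 0.95 for f = 1.25.
- *Day 1 differs from later days* (three visits, Day 7 and Day 8 effects both 1.00). With d = Day 1 effect, reported = w₁d + (1−w₁). For d = 0.25, 0.50, 0.75 this gives 0.75, 0.83, 0.92 (exchangeable, w₁ = 1/3) or 0.67, 0.78, 0.89 (AR(1) with ρ = 0.7, w₁ = 0.435). If Day 1 changes have half the SD of the others at correlation 0.5, the weights are (1, 0, 0) and the reported value is the Day 1 effect itself.

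The two mechanisms can act in opposite directions.

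**4. Effect on the interval.** For exchangeable correlation ρ and T visits, SE(shared)/SE(Day 8) = √[(1+(T−1)ρ)/T]. At ρ = 0.2, 0.5, 0.8 this is 0.683, 0.816, 0.931 for T = 3 and 0.632, 0.791, 0.922 for T = 4.

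Coverage example: 16 subjects, a Day 8 effect of 1 SD, 30% of variance between subjects, exchangeable 0.5 within period, d = 0.5. The bias is 0.833 − 1 = −0.167 and the SE is 0.242, a ratio of −0.69. The nominal 90% interval then covers the true Day 8 difference with probability Φ(1.645+0.69) − Φ(−1.645+0.69) = 0.82. For d = 0.25, 0.75 and 1 the coverage is 0.73, 0.88 and 0.90.

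**5. With the interaction added.** Adding treatment-by-visit, without period-by-visit, gives Day 8 weights of (0, 0, 1). This holds with sequences of 8 and 8 or of 7 and 9.

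**The case against.** The strongest reply is that the interaction was intended and left out of the list by oversight. The model is called an MMRM, one sentence lets effects vary freely over time, and a Day 8 contrast makes little sense without visit-specific treatment means. As a guess about intent this is reasonable. The sentence, however, speaks of each subject and is tied to the covariance matrix, so it does not give treatment a separate mean at each visit. A programmer who follows the list would fit the additive model. Whether or not the interaction was intended, the same edit is needed.

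Some of the other points stand:

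- SAP 7.8.2 summarises serine at each time point, which favours the nominal-time reading of visit. Day 7 predose is then also a trough, so Day 8 is the only trough solely under the window rule. The additive model fails under both readings.
- The illustrations rest on assumed covariances and ratios, and no plasma trough-to-postdose ratio is given. They show sensitivity and do not predict a bias.
- The reach is narrow. The interim rule in SAP 7.12 does not use serine, no serine success criterion exists, Day 8 values are also summarised descriptively, and exposure-response goes to a separate analysis plan.

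These points limit the consequence. They do not reconcile the listed effects with the requested contrast.

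**Conclusion.** The concern holds. As written, the serine MMRM cannot produce a Day 8-specific treatment difference; it reports a covariance-weighted average under a Day 8 label. That conclusion follows from the listed effects alone. The size and direction of any bias cannot be determined from the documents: it is nil if the effect is constant over visits, and can be material if it is not. If treatment has no effect at any visit, the shared coefficient is also zero, so the defect does not create an effect from nothing. The primary EBC analysis has one post-baseline value per period and is unaffected. The point should be fixed, but it does not threaten the trial's main conclusion.

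**What to change.** In SAP 7.8.2:

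- Add treatment-by-visit to the fixed effects and take the pairwise differences and intervals from the Day 8 cell.
- Define visit for this model as the nominal sampling time (Day 1 at 3 to 6 hours, Day 7 predose, Day 7 at 3 to 6 hours, Day 8 predose), and state that the one-value-per-window rule does not apply to it.
- Period-by-visit is optional.

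An equally sound alternative is to fit the 7.8.1 crossover model to the Day 8 change alone.

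The interaction itself is one line of wording and code; the definition of visit adds a sentence. No design change or new data are needed. The Day 8 interval widens because it no longer borrows from other visits. From the step 4 ratios, with exchangeable correlation from 0.8 down to 0.2, the widening is about 7% (1/0.931) to 46% (1/0.683) for three visits and 8.5% (1/0.922) to 58% (1/0.632) for four time points, before any change in degrees of freedom. That is the precision a Day 8 statement actually has.
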